1.3 Schedule of activities (SoA)

The Assessment Schedule (Table 1-2) lists all of the assessments and when they are performed. All data obtained from these assessments must be supported in the participant's source documentation. The "X" in the table denotes the assessments to be recorded in the clinical database or received electronically from a vendor. The "S" in the table denotes the assessments that are only in the participant's source documentation and do not need to be recorded in the clinical database.

Participants should be seen for all visits/assessments as outlined in the Assessment Schedule or as close to the designated day/time as possible. Missed or rescheduled visits should not lead to automatic discontinuation or to a change in the timing of the next scheduled visit (if applicable).

Participants who discontinue from study treatment are to complete the end of treatment visit (Visit 170) procedures as soon as possible, and attend the follow-up visits as indicated in the Assessment Schedule.

Participants who discontinue from study should be scheduled for a final evaluation visit if they agree, as soon as possible, at which time all of the assessments listed for the final visit (Visit 1999) will be performed. At this final visit, all dispensed investigational product should be reconciled, and the adverse events and concomitant medications not previously reported must be recorded on the CRF.

As per Section 4.5, during a public health emergency as declared by local or regional authorities i.e. pandemic, epidemic or natural disaster that limits or prevents on-site study visits, alternative methods of providing continuing care may be implemented by the Investigator as the situation

dictates. If allowable by a local health authority, national and local regulations and depending on operational capabilities, phone calls, virtual contacts (e.g. tele consultation) or visits by site staff/ off-site healthcare professional(s) staff to the participant's home, can replace certain protocol assessments, for the duration of the disruption until it is safe for the participant to visit the site again. If the Investigator delegates tasks to an off-site healthcare professional, the Investigator must ensure the individual(s) is/are qualified and appropriately trained to perform assigned duties. The Investigator must oversee their conduct and remain responsible for the evaluation of the data collected.

Table 1-2 Assessment Schedule

Period	Screening	Placeb	o Run-in	Randomized Treatment								Safety Follow-up	
Visit Name	Screening	Run- In	End of Run- in	Baseline	Week 1 Call	Week 2	Week 4	Week 5 Call	Week 8	Week 9	Week 12 EOT	Week 16	Week 20 EOS
Visit Numbers ¹	1	20	30	100	110	120	130	140	150	160	170	180	1999
Days	-21 to -15	-14	-1 to 0	0	3	14	28	31	56	59 to 63	84	112	140
Informed consent	Χ												
Demography	Х												
Inclusion / Exclusion criteria	Х	Х	X ²										
Physical Examination	Х	X^3	Х			X ³	X ³		X ³	X ³	X	X ³	Х
Body Weight			Х				Х		Х		X	Х	Х
Body Height	Х												
Medical history/current medical conditions	х												
Vital Signs/Office BP	Х												
24-hr Ambulatory BP Monitor			Х							х	х		
Electrocardiogram (ECG)	Х		Х								Х		Х
Pregnancy Test (serum) ⁵	Х		Х								Х		Х
Pregnancy test (urine) ⁵							S		S			S	
Assessment of fertility	S												
Urinalysis	Х		Х			Х	Х		Х		Х	Х	Х
Urine background medication screening sample collection			х								х		
Laboratory evaluations ⁶	Х		Х			X ⁷	X ⁷		X ⁷		Х	X ⁷	Х

Period	Screening	Placeb	o Run-in		zed Treatn	nent						Safety F	ollow-up
Visit Name	Screening	Run- In	End of Run-	Baseline	Week 1 Call	Week 2	Week 4	Week 5 Call	Week 8	Week 9	Week 12 EOT	Week 16	Week 20 EOS
Visit Numbers ¹	1	20	30	100	110	120	130	140	150	160	170	180	1999
Days	-21 to -15	-14	-1 to 0	0	3	14	28	31	56	59 to 63	84	112	140
IWRS/IRT Randomization				Х									
IWRS/IRT Registration	Х	Х	Х			Х	Х		Х	Х	Х	Х	Х
Study drug dispensation/administration		х		х			Х		Х				
Background medication compliance		s	s	s		s	s		s		s		
Adverse Events	Х	Х	Х	X	X	Х	Х	Χ	Х	Х	Χ	Х	Х
Prior/Concomitant Medications	Х	х	х	х	х	х	Х	х	Х	х	х	х	x
Study period completion information			х								Х		Х

Period	Screening	g Placebo Run-in		acebo Run-in Randomized Treatment							Safety Follow-up		
Visit Name	Screening	Run- In	End of Run- in	Baseline	Week 1 Call	Week 2	Week 4	Week 5 Call	Week 8	Week 9	Week 12 EOT	Week 16	Week 20 EOS
Visit Numbers ¹	1	20	30	100	110	120	130	140	150	160	170	180	1999
Days	-21 to -15	-14	-1 to 0	0	3	14	28	31	56	59 to 63	84	112	140

^X Assessment to be recorded in the clinical database or received electronically from a vendor

⁵ Only in women of childbearing potential (as described in Section 8.4.5).

S Assessment to be recorded in the source documentation only

Visit structure given for internal programming purpose only
 Only the entry criteria related to 24-hr ABPM, potassium, eGFR, pregnancy testing in WoCBP, and/or compliance with background treatment as applicable per Section 4.1.

³ Short physical examination.

⁶ Samples must be taken prior to administration of study drug.

⁷ Abbreviated safety lab, as defined in Section 8.4.4

2 Introduction

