Please refer to Section 5.2 for additional blood pressure-related and other exclusion criteria that should be assessed throughout the run-in period.

[figure not shown]
Double-blind Randomized Treatment

The purpose of the Double-blind Randomized Treatment period is to investigate the efficacy and safety of the study treatments in reducing blood pressure when administered on top of optimal or maximally tolerated doses of triple background antihypertensive therapy that the participant was taking at the end of the Run-in Period.

Participants who successfully complete the Run-in Period will complete the procedures of Visit 100 as indicated in Table 1-2 and be randomized into one of the treatment arms per study design (Figure 1-1). The participant will receive the first dose of the blinded study medications on the day of Visit 100.

The double-blind treatment period will consist of 8 scheduled office or phone visits. The timing and the list of the study assessments of each visit can be found in Table 1-2 (Assessment schedule) and detailed in Section 8. For the entire duration of the double-blind treatment period, every attempt should be made so that the participant will continue to take the randomized, double-blind study medication in addition to the background antihypertensive therapy at the doses taken prior and during the Run-in Period with no changes. Also, addition of new antihypertensive medications or increases in the doses of the background antihypertensive therapy are strictly prohibited during the double-blind treatment period. If the participant experiences symptomatic hypotension that the investigator believes necessitates modifications to the participant's background antihypertensive therapy, please refer to Appendix 7 (Section 10.7) for more instructions on how to manage this adverse event.

Modifications to the protocol-specified double-blind study medication regimens are strictly prohibited. Participants who discontinue study medication prematurely should continue to attend study visits and undergo all study procedures as planned. Thus, discontinuation of study medication does not imply discontinuation from the study as a whole, unless the participant withdraws his/her consent for participation.

per the schedule shown in Table 1-2.

Safety follow-up

assessments as well as

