Because XXB750 has a relatively long half-life and might be detectable in the blood for approximately 90 days after the last dose administration, the Safety Follow-up Period is included in the study design to monitor the safety of participants and to ensure they safely transition off the study medication. After completing the procedures of Visit 170, i.e., the final visit of the Double-Blind Treatment Period, the investigator will monitor the participant's health

status and blood pressure to determine the need for modification of the participant's medication regimen. At this point, the investigator may make any modifications to the participant's medication regimen he/she deems necessary, including changes to the participant's background antihypertensive therapy regimen. Two study visits will be conducted to collect safety, assessments and to monitor the participant's blood pressure and

overall health status (i.e., Visit 180 at Week 16 and Visit 1999 at Week 20).

Participants who prematurely discontinue the double-blind study medication will also be required to attend Visits 180 and 1999 to complete the safety follow-up procedures, which will occur 8 and 12 weeks after the last dose administration of XXB750 or its matching placebo.

Remote procedures

At the investigator's direction and based on benefit-risk considerations of the participant's clinical condition, qualifying participants may be offered the option to have certain clinical trial procedures performed at a remote location.

Procedures will be performed remotely under the oversight of the Investigator, who retains accountability for the oversight and all efficacy and safety decisions with delegation of tasks to an off-site healthcare professional.

The remote procedures may be offered in certain countries and sites as determined by Novartis based on national and local regulations.

The off-site healthcare professionals may be provided by a third-party vendor sourced by Novartis. Where a site wishes to use off-site healthcare professionals that are not provided by Novartis this must be agreed with Novartis before use.

In addition to procedures performed by the off-site healthcare professional, the on-site staff may perform certain procedures remotely using tele-visits.

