6.3.3 Emergency breaking of assigned treatment code

Emergency code breaks must only be undertaken when it is required to in order to treat the participant safely.

Most often, discontinuation from study treatment and knowledge of the possible treatment assignments are sufficient to treat a study participant who presents with an emergency condition. Emergency treatment code breaks are performed using the IRT. When the Investigator contacts the system to break a treatment code for a participant, he/she must provide the requested participant identifying information and confirm the necessity to break the treatment code for the participant. The Investigator will then receive details of the investigational drug treatment for the specified participant and a fax or email confirming this information. The system will automatically inform the Novartis monitor for the site and the study team that the code has been broken.

It is the Investigator's responsibility to ensure that there is a dependable procedure in place to allow access to the IRT at any time in case of emergency. The Investigator will provide:

- protocol number
- participant number

In addition, oral and written information to the participant must be provided on how to contact his/her backup in cases of emergency, or when he/she is unavailable, to ensure that un-blinding can be performed at any time.

In case of emergency unblinding, the participant should be discontinued from study treatment and continue with the study visits as scheduled without study medication administration.

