If the participant experiences AEs of hypotension and non-pharmacological interventions were not effective in relieving these AEs, thereby necessitating a modification in the component(s) of the antihypertensive background therapy, please refer to Section 10.7 for instructions on the steps to be taken.

If the investigator decides that, as a last resort for treating the participant it is required to increase the doses of background antihypertensive therapy or to add other antihypertensive medications to a participant's regimen at some point during the 12-week Randomized Treatment Period, an

End of Treatment Visit will be conducted, including a 24-hr ABPM procedure. After that, the study medications can be terminated to allow for introduction of open label antihypertensive therapy according to local standard of care. The participant will continue to attend all remaining study visits as scheduled until the end of the study.

Patients should not take their background antihypertensive medications on the day of clinic visits. Instead they should bring them to the clinic and take them at the appropriate time witnessed by the study staff.

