7.1 Discontinuation of study treatment

Discontinuation of study treatment for a participant occurs when study treatment is permanently stopped for any reason (prior to the planned completion of study treatment administration) and can be initiated by either the participant or the Investigator.

The Investigator must discontinue study treatment for a given participant if he/she believes that continuation would negatively impact the participant's well-being.

Discontinuation from study treatment is required under the following circumstances:

- Participant/guardian decision
- Pregnancy
- Use of prohibited treatment as per recommendations in the prohibited treatment section
- Participants who develop severe uncontrolled hypertension during the study and whose SBP remains >180 mmHg.
- Any situation in which continued study participation might result in an unacceptable safety risk to the participant. This includes adverse events, liver (Section 10.5) and renal (Section 10.6) events as described in the corresponding sections, as well as intolerance to investigational study drugs.
- Following emergency unblinding

The reasons for discontinuation from study treatment must be collected.

^{**}Regular use of bronchodilators for asthma/COPD is acceptable but must be documented.

If discontinuation from study treatment occurs, the Investigator should make a reasonable effort to understand the primary reason for the participant's discontinuation from study treatment and record this information.

Participants who discontinue from study treatment agree to return for the end of treatment and follow-up visits indicated in Section 1.3 Schedule of Assessment.

If the participant cannot or is unwilling to attend any visit(s), the site staff should maintain regular telephone contact with the participant, or with a person pre-designated by the participant. This telephone contact should preferably be done according to the study visit schedule.

After discontinuation from study treatment all efforts should be made to continue follow-up as per study design; at a minimum, in abbreviated visits, the following data should be collected at clinic visits or via telephone/email contact:

- New / concomitant treatments
- Adverse Events / Serious Adverse Events

The Investigator must also contact the IRT to register the participant's discontinuation from study treatment.

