8.3 Efficacy assessments

8.3.1 Ambulatory blood pressure monitoring

The first 24-hour ABPM assessment will be performed at Visit 30 (End of Run-in) and after the participant has met office BP criteria (i.e. msSBP < 180 mmHg and msDBP <110 mmHg). The second and third ABPM assessments will be performed at weeks 9 and week 12 (visit 160 and visit 170/EOT respectively), or earlier in the case of premature permanent discontinuation of blinded study drugs. ABPM assessments may be repeated at any of the visits listed above if there is a quality control finding.

ABPM Procedures

Patients should take their background medications in the clinic witnessed by the investigator or designee (and study medication when applicable) prior to attaching the ABPM device. The ABPM device should be attached to the non-dominant arm of the participant. The application/verification procedures consist of taking several readings using manual prompts to verify that the ABPM device is functioning properly and that no error codes are obtained during the application process. The verification process is not intended for comparison to the clinic reading but rather for confirming that the unit is working properly before prompting the 24-hour period to begin. Following the completion of the verification readings, the investigator or his/her staff would prompt an additional reading to identify the "Beginning of Test" time.

The ABPM unit will be automatically set to measure and record BP every 20 minutes during the day and every 30 minutes during the night.

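### The Week 12 treatment-policy estimand needs a Day 84 ABPM from participants who stop treatment, but the protocol conflicts on whether it is taken

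*Protocol*

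**What the plan says.** **What the analysis needs.** Protocol 3.1 sets the variable at Week 12 and handles discontinuation of study treatment by treatment policy. Protocol 9.3.3 and SAP 2.5.3 use ABPM data collected after stopping. In Table 1-2 the only post-baseline ABPMs are at Visit 160 (Days 59 to 63) and Visit 170 (Day 84).

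**Instructions that bring the ABPM forward.**
- Section 1.3: "Participants who discontinue from study treatment are to complete the end of treatment visit (Visit 170) procedures as soon as possible", after which they attend the follow-up visits.
- Section 8.3.1 places the second and third ABPM at Weeks 9 and 12, "or earlier in the case of premature permanent discontinuation of blinded study drugs".
- Section 4.1 (Safety follow-up) requires early stoppers to attend Visits 180 and 1999, "which will occur 8 and 12 weeks after the last dose administration of XXB750 or its matching placebo".
- Section 7.1 names only the end-of-treatment and follow-up visits. It does add that "all efforts should be made to continue follow-up as per study design; at a minimum, in abbreviated visits, the following data should be collected". That minimum covers concomitant treatments and adverse events, not blood pressure.

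**Instructions that keep the schedule.**
- Section 4.1 (Double-blind Randomized Treatment): "Participants who discontinue study medication prematurely should continue to attend study visits and undergo all study procedures as planned".
- Section 6.3.3, after emergency unblinding: "the participant should be discontinued from study treatment and continue with the study visits as scheduled without study medication administration".
- Section 6.8.1, when antihypertensive therapy must be increased or added: an end-of-treatment visit with ABPM is held, then "the study medications can be terminated to allow for introduction of open label antihypertensive therapy according to local standard of care", and "The participant will continue to attend all remaining study visits as scheduled until the end of the study".
- Section 8 (opening text) times all visits from Visit 100. Its sentence on stoppers can be read either way.

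**The concern.** A treatment-policy estimand at a fixed time needs the outcome measured at that time whether or not treatment continued. If Visit 170 is used up at the stopping date and only Visits 180 and 1999 remain, the Day 84 ABPM is never taken and no analysis can recover it. For those who stop before Week 9, the Week 9 ABPM goes too. That reading enters the imputation model and the second secondary endpoint.

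SAP 2.5.3 imputes missing values after an intercurrent event from participants in the same arm who had the same type of event and an observed endpoint. Without such donors it pools lower doses, then uses placebo participants with copy reference. The result for stoppers would then rest on the fallback and not on observed data.

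Even a site that takes both recordings has no stated label for the second one once Visit 170 has been used. SAP 2.1.1 generally excludes ABPM from unscheduled visits.

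**Working it through.** **1. The plan's own figures.** With SD 12 mmHg, 30 per arm, a maximum effect of 10 mmHg and one-sided 2.5% (Protocol 9.9.1), simulated MCP-Mod power for the five candidate shapes is 92.6%, 91.8%, 95.8%, 95.4% and 93.3%. The minimum is 91.8%, against 92% stated. Pairwise power is 89.8% (normal) or 88.8% (t), against about 89% stated. Sample size: 150 / 0.9 = 166.7, so 167, against 170 planned. These figures are sound and do not bear on this point. The 10% in 9.9.1 is loss to follow-up, not treatment stopping.

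**2. Visit days for early stoppers.** Section 4.1 (Safety follow-up) puts Visit 180 at last dose + 56 days and Visit 1999 at last dose + 84 days. The SAP's on-treatment limit is last dose + 28 days (2.1.1).

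| Doses received | Last dose | Visit 180 | Visit 1999 | Last dose to Day 84 | Past 28-day limit at Day 84 |
|---|---|---|---|---|---|
| 1 | Day 0 | Day 56 | Day 84 | 84 days | 56 days |
| 2 | Day 28 | Day 84 | Day 112 | 56 days | 28 days |
| 3 | Day 56 | Day 112 | Day 140 | 28 days | 0 days |

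After three doses the days match Table 1-2. After one or two doses, Day 84 falls on Visit 1999 or Visit 180, and neither has an ABPM. Section 8 (opening text) instead times both visits from Visit 100. The two rules cannot both hold for one- and two-dose stoppers.

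**3. Does the SAP settle it?**
- SAP 2.1.1 places end of treatment at Week 12 for completers and derives a separate date for stoppers.
- Protocol 9.3.7 (item 4) and SAP 2.5.7 (item 4) let an end-of-treatment or last on-treatment value stand for Week 12 only in a supplementary analysis.
- The implication is that an early reading is not a Week 12 value in the primary analysis, but this is not stated, and the text available gives no Week 12 window.
- SAP 2.5 takes the valid reading closest to the scheduled date, which helps only if a Day 84 reading exists.

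**4. Possible donors per arm (34 randomized, stopping rate assumed).**
- ABPM brought forward at all sites: 0.
- Schedule kept at all sites: at most 34 × 0.10 = 3.4, or 34 × 0.20 = 6.8.
- In total: 170 × 0.10 = 17, or 170 × 0.20 = 34.

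**5. Illustration only: a lone early reading counted as Week 12.** Let q be the share stopping and r the share of the 10 mmHg effect present at Week 12, both assumed. Overstatement = 10 × q × (1 − r) mmHg.

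| q | r = 0 | r = 0.5 | r = 1 | r = 1.2 |
|---|---|---|---|---|
| 10% | 1.0 | 0.5 | 0 | −0.2 |
| 20% | 2.0 | 1.0 | 0 | −0.4 |

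This assumes the full 10 mmHg at the early reading and ignores placebo stoppers. Open-label therapy, whose effect the estimand includes, could bring r to 1 or above. For any one participant this scenario and imputation from the fallback are alternatives; they do not add up.

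**The case against.** The strongest reply is that Section 4.1 addresses this case directly and keeps all procedures, and that nothing in 1.3 cancels Day 84. An early end-of-treatment visit followed by the remaining schedule is a natural reading, and 6.8.1 sets out that order. The follow-up timing in 4.1 moves only Visits 180 and 1999. That they coincide with Day 84 matters only if Visit 170 is treated as already used.

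This reading is plausible, and probably the one intended. But no passage says that a second ABPM is done at Day 84 after an early Visit 170, and 6.8.1 leaves open whether Visit 170 still counts as remaining. Sections 1.3 and 8.3.1, which schedule this measurement, point the other way.

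Three further points stand in part:
- Sparse donors are foreseen. SAP 2.5.3 prespecifies a fallback, and 2.5.6 adds placebo-based imputation after AE or death. Even with full retention, an arm of 34 at 10% stopping has a 33% chance of two or fewer stoppers. A foreseen fallback still does not justify leaving the collection of obtainable data unclear.
- A Week 12 window may exist in redacted text or in the programming specifications, so its absence cannot be asserted.
- The mmHg illustration uses assumed inputs and is not evidence of bias. Zero donors is a limiting case that requires every site to take the first reading.

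**Conclusion.** The concern holds. The protocol contradicts itself on whether the primary endpoint is measured at Day 84 in participants who stop treatment, and the available SAP text does not resolve it. Donors for the retrieved-dropout step range from 0 per arm to about 3.4 (assumed 10% stopping) or 6.8 (assumed 20%), depending on which section sites follow. The documents give no stopping rate, so the size and direction of any bias are unknown. The SAP's own trigger for the while-on-treatment analysis, more than 10% of the FAS (more than 17 if all 170 are included), is a threshold and not a forecast. Sample size and power stand. This should be fixed. Confidence is medium, because the schedule-keeping reading is tenable and a window may exist in text not seen.

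**What to change.** - **Protocol 1.3, 4.1, 7.1, 8 and 8.3.1:** reconcile them so that participants who stop treatment but stay in the study keep the Week 9 and Week 12 ABPM timed from Visit 100. Record the early end-of-treatment assessment under its own visit label.
- **Protocol 4.1 and 8:** reconcile the two timing rules for Visits 180 and 1999 (from last dose, or from Visit 100).
- **SAP 2.5:** state that only an ABPM within a defined window around Day 84 counts as Week 12 in the primary analysis, and that an early end-of-treatment ABPM enters only the while-on-treatment analysis. If the programming specifications already hold the window, cite it.

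The cost is clarifying text and one further ABPM recording per early stopper: about 17 in total at an assumed 10% stopping, or 34 at 20%. Section 4.1 already intends the Day 84 recording.
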